7.1.1 Risks Associated with Ramucirumab

Potential risks and toxicities of ramucirumab are detailed in the manufacturer's package insert (https://www.accessdata.fda.gov/drugsatfda_docs/label/2014/125477s002lbl.pdf).

7.1.2 Dose Modification for Ramucirumab

Infusion-Related Reactions (IRR):

- Reduce infusion rate by 50% of grade 1 or 2 IRR.
- Grade 1 or 2 IRR should receive pre-medication with dexamethasone and acetaminophen prior to subsequent infusions.
- Grade 3 or 4 IRR: Discontinue ramucirumab.

Hypertension

PROTOCOL NUMBER: OSU-19132

- Hold ramucirumab for severe hypertension (Uncontrolled or poorly-controlled hypertension (>160 mmHg systolic or >100 mmHg diastolic) until controlled with medical management.
- Discontinue ramucirumab for severe hypertension (>160 mmHg systolic or >100 mmHg diastolic for >4 weeks) that cannot be controlled with antihypertensive therapy.

Proteinuria:

- If a patient has proteinuria with 24 hour urine protein ≥ 2 g, ramucirumab should be held. When level returns to less than 2 g/24 hr, may resume at a reduced dose of 8 mg/kg every 3 weeks. If level 2 g/24 hr or greater recurs, interrupt therapy again, and when level returns to less than 2 g/24 hr, resume at a reduced dose of 6 mg/kg every 3 weeks.
- For nephrotic syndrome or urine protein > 3 g/24 hr, ramucirumab should be permanently discontinued.

Wound Healing:

- Hold ramucirumab prior to surgery and until the wound is fully healed.

Indications for permanent discontinuation of Ramucirumab

- IRR: Patients with grade 3 or 4 infusion-related reactions must not receive further treatment with ramucirumab.
- Hypertension: Patients with grade 4 hypertension must not receive further treatment with Ramucirumab.
- Proteinuria: The patient will have ramucirumab permanently discontinued if the protein level is >3 g/24 hours, if there is a third occurrence of >2 g/24 hours, or if the protein level does not return to <2 g/24 hours within 2 weeks.
- Thromboembolism: Grade 3 and 4 arterial thromboembolic events, or any PE/DVT occurring or worsening during anticoagulant therapy, require permanent discontinuation of ramucirumab therapy. Any venous or arterial event leading to discontinuation of ramucirumab therapy will be considered serious and should be reported via the serious adverse event (SAE) mechanism.
- Hepatic disease: Any patient who experiences signs of hepatic encephalopathy or other serious signs of liver impairment such as hepatorenal syndrome must be permanently discontinued from ramucirumab therapy.
- Ramucirumab should be permanently discontinued in the event of a gastrointestinal perforation or fistula formation.
- If Reversible Posterior Leukoencephalopathy (RPLS) is diagnosed, ramucirumab must be permanently discontinued. All cases of RPLS must be reported via the SAE mechanism.

For all other toxicities, ramucirumab may be held for up to 42 days. If toxicity does not improve to grade 1 or better within 21 days, discontinue ramucirumab.

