4.5 Patient Removal from Study Treatment

Patients may be removed from the study treatment at any time for the following reasons:

- Disease progression
- Noncompliance with study procedures
- Need of treatment with medications not allowed by the study protocol
- The participant or participant's legally acceptable representative requests to discontinue study treatment
- Intercurrent illness that interferes with study assessments
- Incidence or severity of AEs in this study indicates a potential health hazard to the patient (Investigator discretion)
- Pregnancy
- At the discretion of the treating investigator after discussion with principal investigator
- Termination of the study by the Investigator or pharmaceutical company
- Ramucirumab specific criteria for end of study treatment:
 - Grade 3 and 4 arterial thromboembolic events, or any PE/DVT occurring or worsening during anticoagulant therapy, require permanent discontinuation of ramucirumab therapy. Any venous or arterial event leading to discontinuation of ramucirumab therapy will be considered serious and should be reported via the serious adverse event (SAE) mechanism.
 - Any patient who experiences signs of hepatic encephalopathy or other serious signs of liver impairment such as hepatorenal syndrome must be permanently discontinued from ramucirumab therapy.
 - The patient will have ramucirumab permanently discontinued if the protein level is >3 g/24 hours, if there is a third occurrence of >2 g/24 hours, or if the protein level does not return to <2 g/24 hours within 2 weeks.
 - Patients with grade 4 hypertension must not receive further treatment with Ramucirumab. Patients with grade 3 or 4 infusion-related reactions must not receive further treatment with ramucirumab.
 - Ramucirumab should be permanently discontinued in the event of a gastrointestinal perforation or fistula formation.
 - If Reversible Posterior Leukoencephalopathy (RPLS) is diagnosed, ramucirumab must be permanently discontinued. All cases of RPLS must be reported via the SAE mechanism.

IRB Protocol Number: 2019C0145
IRB Approval date: 06/10/2022
Version: 05/06/2022

PROTOCOL NUMBER: OSU-19132

- Completion of 35 treatments (approximately 2 years) with ramucirumab.
- Pembrolizumab specific criteria for end of study treatment (detailed in Table 5):
 - Recurrent grade 3 toxicity
 - Recurrent Grade 2 pneumonitis
 - Grade 4 toxicity, except for endocrinopathies (as detailed in Table 5)

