6.3.5 Tumor Imaging on Study

The first on-study imaging assessment should be performed at 6 weeks (42 days \pm 7 days) from the date of allocation. Subsequent tumor imaging should be performed every 6 weeks (42 days \pm 7 days) or more frequently if clinically indicated. After 6 months, participants who remain on treatment will have imaging performed every 12 weeks (84 days \pm 7 days). Imaging timing should follow calendar days and should not be adjusted for delays in cycle starts. Imaging should continue to be performed until disease progression is identified by the Investigator.

Objective response should be confirmed by a repeat imaging assessment. Tumor imaging to confirm PR or CR should be performed at least 4 weeks after the first indication of a response is observed. Participants will then return to regular scheduled imaging every 6 weeks, starting with the next scheduled imaging time point. Participants who receive additional imaging for confirmation do not need to undergo the next scheduled tumor imaging if it is less than 4 weeks later; tumor imaging may resume at the subsequent scheduled imaging time point.

PROTOCOL NUMBER: OSU-19132

Per iRECIST (Appendix 2), disease progression should be confirmed by the site 4 to 8 weeks after first radiologic evidence of PD in clinically stable participants as defined by Appendix 2 (Note- if patient is receiving clinical benefit, oligoprogressive CNS disease that can be controlled with local therapy such as stereotactic radiation, may continue on treatment beyond progression with PI approval. Ramucirumab should be held for 2 weeks prior to radiation. Patient can have radiation for CNS oligoprogression as long as ramucirumab is held for 4-6 weeks afterwards. Ramucirumab can be restarted after this time if the patient is asymptomatic, clinically stable and this is considered appropriate by the investigator.). Participants who have unconfirmed disease progression may continue on treatment at the discretion of the Investigator until progression is confirmed by the site provided they have met the conditions detailed in Section 9.2.1.6. Participants who receive confirmatory imaging do not need to undergo the next scheduled tumor imaging if it is less than 4 weeks later; tumor imaging may resume at the subsequent scheduled imaging time point, if clinically stable. Participants who have confirmed disease progression by iRECIST, as assessed by the site, will discontinue study treatment.

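### Ramucirumab has no bleeding rule: a grade 3-4 bleed that settles within 21 days never triggers a mandatory stop

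*Combined protocol and SAP*

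**What the plan says.** Section 1.5.1, in its account of the phase III docetaxel-ramucirumab trial, gives hypertension and bleeding as the main toxicities related to ramucirumab.

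The rules for stopping or holding ramucirumab are in two places. Section 4.5 has a list headed "Ramucirumab specific criteria for end of study treatment". Section 7.1.2 covers dose modification and repeats the permanent-stop items. Between them they address infusion reactions, hypertension, proteinuria, wound healing, thromboembolism, hepatic disease, GI perforation or fistula, reversible posterior leukoencephalopathy and, in 4.5, completion of 35 treatments. Neither has an item for bleeding.

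Section 7.1.2 closes with a catch-all in two sentences: "For all other toxicities, ramucirumab may be held for up to 42 days", and "If toxicity does not improve to grade 1 or better within 21 days, discontinue ramucirumab".

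Bleeding does appear in the eligibility criteria. Exclusion criterion 6 bars patients with grade 3-4 GI bleeding in the 3 months before the first dose. Criteria 9 and 10 deal with CNS hemorrhage and hemoptysis.

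**The concern.** One of the two toxicities that the protocol singles out for this drug has no rule of its own once treatment starts. The catch-all responds to time to recovery only; peak grade, site and recurrence play no part. A life-threatening bleed brought under control in a few days is thus handled like any other toxicity that resolves promptly.

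Patient safety is what is at stake. Bleeding risk on study is not negligible by design: full-dose anticoagulation is allowed (Table 3, footnote c), as is daily aspirin up to 325 mg (exclusion criterion 8 and section 8.4). Section 3.1.4 also foresees more sites if stage 1 succeeds, so handling could vary between investigators who all follow the same text.

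**Working it through.** The plan states no figure to reproduce. The check applies the written rules to a bleed and compares the result with neighboring rules.

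**1. Which rule governs.** A bleed caused by GI perforation or fistula is caught by that permanent-stop item. A bleed that leads to surgery meets the instruction to hold ramucirumab until the wound has healed, which is a hold and not a stop. The grade 4 and recurrent grade 3 items in 4.5 belong to the pembrolizumab list and refer to Table 5; even read broadly, they would stop pembrolizumab, and section 7.3 lets the other drug continue. Any other bleed goes to the catch-all.

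**2. What the catch-all requires after a grade 3-4 bleed.**

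| Course of the bleed | Hold | Stop |
|---|---|---|
| Not at grade 1 or better within 21 days | optional in wording | mandatory |
| Grade 1 or better within 21 days | optional in wording | none |
| Second bleed, again settled within 21 days | optional in wording | none |

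**3. Comparison with the entry rule.** Cycles are 21 days.
- With no dose skipped, the next infusion falls at most 21 days after the bleed (24 with the 3-day dosing window).
- The longest delay compatible with the catch-all arises if the bleed occurs on a dosing day and the 42 days run from the next scheduled dose: 21 + 42 = 63 days (66 with the window).
- Criterion 6 bars a first dose for 3 months, roughly 90 days.

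So any resumption after an on-study grade 3-4 GI bleed under the catch-all comes sooner than the protocol would allow a first dose after the same event.

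**4. Comparison with other ramucirumab rules.** Where the authors wanted a definite action, they wrote one:
- Permanent stop whatever the recovery: "Patients with grade 3 or 4 infusion-related reactions must not receive further treatment with ramucirumab" and "Grade 3 and 4 arterial thromboembolic events, or any PE/DVT occurring or worsening during anticoagulant therapy, require permanent discontinuation of ramucirumab therapy".
- Directive hold: "Hold ramucirumab for severe hypertension", which lasts until blood pressure is controlled.
- Condition for resuming: for proteinuria, "When level returns to less than 2 g/24 hr, may resume at a reduced dose of 8 mg/kg every 3 weeks"; after CNS radiation (section 6.3.5), "Ramucirumab can be restarted after this time if the patient is asymptomatic, clinically stable and this is considered appropriate by the investigator".

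**5. Other routes off the drug.** The health-hazard item in 4.5 is marked as investigator discretion, and section 6.6 allows removal to protect a patient's health. Section 7.1.1 cites the package insert for risks, not as a dosing rule. SAE reporting (13.5.3) and committee review (6.2) set no action for the next dose. None of these requires a stop.

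**The case against.** The best defense is that the catch-all is a real rule. Its ordinary reading is to hold, to resume on recovery to grade 1 or better, and to stop otherwise; no sensible investigator would infuse an anti-VEGFR-2 antibody during an active grade 3-4 bleed. Discretionary removal is available, and toxicity is reviewed at least monthly. The entry rule also answers a different question, since a patient who is already benefiting has more to lose by stopping. Much of this stands, and it limits the point to the missing mandatory stop.

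Four stronger readings are tempting, but the documents do not support them.
- *Nothing governs resumption after a bleed.* The catch-all implies recovery to grade 1 or better.
- *Bleeding departs from a uniform grade 3-4 stop.* There is no such rule: on grade alone, hypertension stops the drug only at grade 4, and PE/DVT only if it occurs or worsens during anticoagulation.
- *Severe bleeding is known to be frequent with this regimen.* The statement in 1.5.1 concerns ramucirumab with docetaxel and gives neither grade nor frequency. For ramucirumab with pembrolizumab, sections 1.3.1 and 1.5.2 report no new concerning safety signals.
- *The chance of the event can be put at some figure.* It cannot. If one merely assumed a 1% to 5% risk of grade 3-4 bleeding, with 50% to 90% settling within 21 days, the chance of at least one such patient among 34 would run from 1 - (1 - 0.005)^34 = 15.7% to 1 - (1 - 0.045)^34 = 79.1%. Neither input has a source in the documents, the range is too wide to inform a decision, and it does not address actual re-dosing.

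Nor do the documents show that bleeds below grade 3 need a separate rule; that is for the safety physician to judge.

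**Conclusion.** The point holds as a gap in the written rules. A grade 3-4 bleed not due to GI perforation or fistula never triggers a mandatory ramucirumab stop if it reaches grade 1 or better within 21 days, and the hold in the meantime is optional in wording. For GI bleeds this is inconsistent with exclusion criterion 6.

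The protocol permits re-dosing in this situation; it does not call for it, and many investigators would probably stop. The conclusion rests on the text alone and needs no assumed event rate. How often the situation would arise cannot be estimated. The primary endpoint is not affected, and the tolerability analysis is descriptive. This is a cheap improvement in patient safety, not a flaw in the trial's inference.

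**What to change.** Add one item to the ramucirumab lists in sections 4.5 and 7.1.2:

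> Bleeding: permanently discontinue ramucirumab for grade 3 or 4 bleeding assessed as possibly, probably or definitely related to study treatment. For grade 3 or 4 bleeding assessed as unrelated or unlikely related, hold ramucirumab until grade 1 or better, within the existing time limits.

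The split follows the attribution categories in section 9.4.2. That section reserves the word toxicity for related events, so the second sentence also removes any doubt about whether the catch-all reaches an unrelated bleed.

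The cost is two list entries, with no added visits, tests or patients. The downside is that a few patients stop ramucirumab earlier than they otherwise would. They may continue pembrolizumab under section 7.3, and they remain evaluable for response, because section 9.4.2 requires only that an eligible patient has received at least one dose.

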7.1.3 Reproductive risks

Because the teratogenicity of ramucirumab and pembrolizumab is not known, the patient, if sexually active, must be postmenopausal, surgically sterile, or using effective contraception (hormonal or barrier methods).

PROTOCOL NUMBER: OSU-19132

Patients should not become pregnant or father a baby while on this study because the drugs in this study can affect an unborn baby. Women should not breastfeed a baby while on this study. It is important patients understand the need to use birth control while on this study. Female patients of child-bearing potential must agree to use dual methods of contraception and have a negative serum pregnancy test at screening (\leq 14 days prior to first dose) and negative urine pregnancy test on day 1 of study drug. Male patients must use an effective barrier method of contraception if sexually active with a female of child-bearing potential. Acceptable methods of contraception are condoms with contraceptive foam, oral, implantable or injectable contraceptives, contraceptive patch, intrauterine device, diaphragm with spermicidal gel, or a sexual partner who is surgically sterilized or post-menopausal. Total (true) abstinence (when this is in line with the preferred and usual lifestyle of the patient), is an acceptable method of contraception. Periodic abstinence (e.g., calendar, ovulation, symptothermal, post- ovulation methods) and withdrawal are not acceptable methods of contraception. For both male and female patients, effective methods of contraception must be used throughout the study and for three months following the last dose.

7.2 Pembrolizumab Toxicity Overview

Pembrolizumab is currently approved by the Food and Drug Administration (FDA) for commercial use as a single agent and in combination with cytotoxic chemotherapy for non-small cell lung cancer. The combination of pembrolizumab with ramucirumab is investigational. The entire safety profile of the combination therapy is not known at this time. Measures will be taken to ensure the safety of the patients participating in this trial, including the use of stringent inclusion and exclusion criteria and close monitoring. Toxicity grading will be performed in accordance with NCI CTCAE version 5.0. If more than one different type of toxicity occurs concurrently, the most severe grade will determine the modification.

If toxicities are encountered, adjustments will be made to the study treatment as detailed in the sections below. All AEs and SAEs will be recorded during the trial and for up to 30 days after the last dose of study treatment or until the initiation of another anti-cancer therapy, whichever occurs first.

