7.2.2 Dose Modifications for Pembrolizumab

Pembrolizumab may be held up to 12 weeks for immune-related toxicity. If a patient has an immune-related toxicity that does not resolve within 12 weeks, pembrolizumab will be discontinued

AEs associated with pembrolizumab exposure may represent an immunologic etiology. These immune-related AEs (irAEs) may occur shortly after the first dose or several months after the last dose of pembrolizumab treatment and may affect more than one body system simultaneously. Therefore, early recognition and initiation of treatment is critical to reduce complications. Based on existing clinical study data, most irAEs were reversible and could be managed with interruptions of pembrolizumab, administration of corticosteroids and/or other supportive care.

PROTOCOL NUMBER: OSU-19132

For suspected irAEs, ensure adequate evaluation to confirm etiology or exclude other causes. Additional procedures or tests such as bronchoscopy, endoscopy, skin biopsy may be included as part of the evaluation. Based on the severity of irAEs, withhold or permanently discontinue pembrolizumab and administer corticosteroids. Dose modification and toxicity management guidelines for irAEs associated with pembrolizumab are provided below in Table 5.

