7.3 Study Drug Discontinuation

If either ramucirumab or pembrolizumab is held or discontinued for toxicity, the remaining drug may be continued as maintenance therapy for up to 35 cycles or disease progression or unacceptable toxicity.

PROTOCOL NUMBER: OSU-19132

Table 5. Dose modifications and toxicity management guidelines for immune-related AEs associated with pembrolizumab

General instructions:				
Immune-related AEs	Toxicity grade or conditions (CTCAEv5.0)	Action taken to pembrolizumab	irAE management with corticosteroid and/or other therapies	Monitor and follow-up
Pneumonitis	Grade 2	Withhold	
 Administer corticosteroids (initial dose of 1-2 mg/kg prednisone or equivalent) followed by taper 	
 Monitor participants for signs and symptoms of pneumonitis Evaluate participants with suspected pneumonitis with radiographic imaging and initiate corticosteroid treatment Add prophylactic antibiotics for opportunistic infections
	Grade 3 or 4, or recurrent Grade 2	Permanently discontinue		
Diarrhea / Colitis	Grade 2 or 3	Withhold	
 Administer corticosteroids (initial dose of 1-2 mg/kg prednisone or equivalent) followed by taper 	
 Monitor participants for signs and symptoms of enterocolitis (ie, diarrhea, abdominal pain, blood or mucus in stool with or without fever) and of bowel perforation (ie, peritoneal signs and ileus). Participants with \geq Grade 2 diarrhea suspecting colitis should consider GI consultation and performing endoscopy to rule out colitis. Participants with diarrhea/colitis should be advised to drink liberal quantities of clear fluids. If sufficient oral fluid intake is not feasible, fluid and electrolytes should be substituted via IV infusion.
	Recurrent Grade 3 or Grade 4	Permanently discontinue		

CONFIDENTIAL

PROTOCOL NUMBER: OSU-19132

AST / ALT elevation or Increased bilirubin	Grade 2	Withhold	
 Administer corticosteroids (initial dose of 0.5- 1 mg/kg prednisone or equivalent) followed by taper 	
 Monitor with liver function tests (consider weekly or more frequently until liver enzyme value returned to baseline or is stable)
	Grade 3 or 4	Permanently discontinue	
 Administer corticosteroids (initial dose of 1-2 mg/kg prednisone or equivalent) followed by taper 	

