Type 1 diabetes mellitus (T1DM) or Hyperglycemia	Newly onset T1DM or Grade 3 or 4 hyperglycemia associated with evidence of β -cell failure	Withhold	
 Initiate insulin replacement therapy for participants with T1DM Administer anti-hyperglycemic in participants with hyperglycemia 	
 Monitor participants for hyperglycemia or other signs and symptoms of diabetes.
Hypophysitis	Grade 2	Withhold	
 Administer corticosteroids and initiate hormonal replacements as clinically indicated. 	
 Monitor for signs and symptoms of hypophysitis (including hypopituitarism and adrenal insufficiency)
	Grade 3 or 4	Withhold or permanently discontinue ¹		
Hyperthyroidism	Grade 2	Continue	
 Treat with non-selective beta-blockers (eg, propranolol) or thionamides as appropriate 	
 Monitor for signs and symptoms of thyroid disorders.
	Grade 3 or 4	Withhold or permanently discontinue ¹		

PROTOCOL NUMBER: OSU-19132

Hypothyroidism	Grade 2-4	Continue	
 Initiate thyroid replacement hormones (eg, levothyroxine or liothyroinine) per standard of care 	
 Monitor for signs and symptoms of thyroid disorders.
Nephritis and Renal dysfunction	Grade 2	Withhold	
 Administer corticosteroids (prednisone 1-2 mg/kg or equivalent) followed by taper. 	
 Monitor changes of renal function
	Grade 3 or 4	Permanently discontinue		
Myocarditis	Grade 1 or 2	Withhold	
 Based on severity of AE administer corticosteroids 	
 Ensure adequate evaluation to confirm etiology and/or exclude other causes
	Grade 3 or 4	Permanently discontinue		
All other immune-related AEs	Intolerable/persistent Grade 2	Withhold	
 Based on type and severity of AE administer corticosteroids 	
 Ensure adequate evaluation to confirm etiology and/or exclude other causes
	Grade 3	Withhold or discontinue based on the type of event. Events that require discontinuation include and not limited to: Gullain-Barre Syndrome, encephalitis		
	Grade 4 or recurrent Grade 3	Permanently discontinue		

PROTOCOL NUMBER: OSU-19132

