1. Withhold or permanently discontinue pembrolizumab is at the discretion of the investigator or treating physician.

NOTE:

For participants with Grade 3 or 4 immune-related endocrinopathy where withhold of pembrolizumab is required, pembrolizumab may be resumed when AE resolves to \leq Grade 2 and is controlled with hormonal replacement therapy or achieved metabolic control (in case of T1DM).

Table 6. Pembrolizumab Infusion Reaction Dose modification and Treatment Guidelines

PROTOCOL NUMBER: OSU-19132

NCI CTCAE Grade	Treatment	Premedication at Subsequent Dosing
Grade 1 Mild reaction; infusion interruption not indicated; intervention not indicated	Increase monitoring of vital signs as medically indicated until the participant is deemed medically stable in the opinion of the investigator.	None
Grade 2 Requires therapy or infusion interruption but responds promptly to symptomatic treatment (e.g., antihistamines, NSAIDs, narcotics, IV fluids); prophylactic medications indicated for ≤ 24 hrs	
Stop Infusion. Additional appropriate medical therapy may include but is not limited to: IV fluids Antihistamines NSAIDs Acetaminophen Narcotics
 
Increase monitoring of vital signs as medically indicated until the participant is deemed medically stable in the opinion of the investigator.
 
If symptoms resolve within 1 hour of stopping drug infusion, the infusion may be restarted at 50% of the original infusion rate (e.g. from 100 mL/hr to 50 mL/hr). Otherwise dosing will be held until symptoms resolve and the participant should be premedicated for the next scheduled dose.
 
Participants who develop Grade 2 toxicity despite adequate premedication should be permanently discontinued from further study drug treatment
	Participant may be premedicated 1.5h (± 30 minutes) prior to infusion of _____ with: Diphenhydramine 50 mg po (or equivalent dose of antihistamine). Acetaminophen 500- 1000 mg po (or equivalent dose of analgesic).
Grades 3 or 4 Grade 3: Prolonged (i.e., not rapidly responsive to symptomatic medication and/or brief interruption of infusion); recurrence of symptoms following initial improvement;	
Stop Infusion. Additional appropriate medical therapy may include but is not limited to: Epinephrine** IV fluids Antihistamines NSAIDs Acetaminophen Narcotics Oxygen Pressors
	No subsequent dosing

PROTOCOL NUMBER: OSU-19132

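### The rule that the highest grade decides for concurrent toxicities (1.4, 7.1, 7.2) conflicts with Table 5: read literally, grade 4 hyperglycemia turns a permanent pembrolizumab stop for a first grade 3 organ event into a hold

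*Combined protocol and SAP*

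**What the plan says.** Sections 1.4, 7.1 and 7.2 carry the same sentence: "If more than one different type of toxicity occurs concurrently, the most severe grade will determine the modification". Sections 1.4 and 7.2 then add that adjustments follow the detail given further on.

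For pembrolizumab that detail is Table 5, printed under Section 7.3. It assigns an action to each combination of toxicity and grade:

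- **Pneumonitis:** permanent discontinuation at "Grade 3 or 4, or recurrent Grade 2"; a hold at a first grade 2.
- **Diarrhea/colitis:** a hold at a first grade 2 or 3; permanent discontinuation at "Recurrent Grade 3 or Grade 4".
- **Hepatic, renal, myocarditis:** permanent discontinuation at grade 3 or 4.
- **Diabetes/hyperglycemia:** "Newly onset T1DM or Grade 3 or 4 hyperglycemia associated with evidence of" beta-cell failure is a hold. This row has no permanent stop.

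A note after the tables adds: "For participants with Grade 3 or 4 immune-related endocrinopathy where withhold of pembrolizumab is required, pembrolizumab may be resumed when AE resolves" to grade 2 or lower and is controlled. Section 7.2.2 sets the limit: "Pembrolizumab may be held up to 12 weeks for immune-related toxicity". It also foresees concurrent events, saying that immune-related events "may affect more than one body system simultaneously".

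Section 4.5 lists pembrolizumab end-of-treatment criteria and refers to Table 5. It names recurrent grade 3 toxicity, recurrent grade 2 pneumonitis, and grade 4 toxicity other than endocrinopathies.

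**The concern.** A rule that lets the highest grade decide is safe only if a higher grade never carries a milder action. Table 5 is not ordered that way across rows. A patient with grade 4 hyperglycemia and grade 3 pneumonitis therefore gets two instructions for the same drug: hold under the concurrent-toxicity sentence, and stop for good under the pneumonitis row. The visible text does not say which prevails. At stake is whether a patient who has met a permanent stop criterion could, on the letter of the protocol, be restarted on pembrolizumab. The sentence exists to govern concurrent events, and in these cases it gives the less protective answer.

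**Working it through.** The plan gives no figure to reproduce. The check compares Table 5 cell by cell with the sentence.

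**1. Cells.** H = hold, S = permanent stop. Cells left to the investigator's discretion, cells that continue treatment, and the row for all other immune-related events are left out at first.

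| Row | G1 | G2 | G3 | G4 | Recurrent |
|---|---|---|---|---|---|
| Pneumonitis | – | H | S | S | G2: S |
| Colitis | – | H | H | S | G3: S |
| Hepatic | – | H | S | S | – |
| Renal | – | H | S | S | – |
| Myocarditis | H | H | S | S | – |
| Hyperglycemia | – | – | H | H | – |
| Hypophysitis | – | H | – | – | – |

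This gives 3+3+3+3+4+2+1 = 19 first-occurrence cells, and 21 with the two recurrence cells.

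**2. Pairs of different toxicities at unequal grades.** Formula: all pairs, minus same-row pairs, minus equal-grade pairs across rows.

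- First occurrence: 171 − 19 − (15+15+15) = 107.
- With recurrence: 210 − 25 − (20+20+15) = 130.

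Equal-grade pairs are excluded. The sentence is silent there, which is a gap and not a contradiction.

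**3. Reversals (hold at the higher grade, stop at the lower).** The only grade 4 hold is hyperglycemia. The grade 3 holds are colitis and hyperglycemia. The only grade 2 stop is recurrent pneumonitis.

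- Grade 4 hyperglycemia over a first grade 3 pneumonitis, hepatic, renal or myocarditis event: 4.
- Grade 4 hyperglycemia over recurrent grade 3 colitis: 1.
- Grade 3 or 4 hyperglycemia over recurrent grade 2 pneumonitis: 2.
- First grade 3 colitis over recurrent grade 2 pneumonitis: 1.

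Totals: 4 of 107 without recurrence cells, 8 of 130 with them.

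**4. Against Section 4.5.** The last three bullets of step 3 (1+2+1 = 4 pairings) concern stops that 4.5 names separately. The first four do not: a first grade 3 organ event is a stop in 4.5 only through its reference to Table 5. These four are the core case.

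**5. Sensitivity to coding.** Adding the fixed cells of the row for other immune-related events gives 9 of 173. The ninth is grade 4 hyperglycemia over a recurrent grade 3 event, which 4.5 also names. If continuing treatment is counted as a modification, the thyroid rows raise the totals to 26 of 161 without recurrence and 33 of 189 with it.

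**6. What must happen before pembrolizumab is resumed.** Start at hyperglycemia grade 4 and organ event grade 3, and assume grades are reassessed over time.

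- Hyperglycemia falls to 3 while the organ event is still 3: a tie. The sentence is silent and the organ row's stop applies.
- Hyperglycemia falls to 2 while the organ event is still 3: the organ event is now the highest grade, and its stop applies.
- The organ event falls below 3 while hyperglycemia is still 4: the literal rule keeps the hold. Resumption then needs hyperglycemia at grade 2 or lower and controlled, and the organ event at grade 1 or lower. Myocarditis must have resolved, because its own row holds at grade 1.

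Only the third path ends in resumption. The 12-week limit leaves time for it.

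**7. Ramucirumab.** Section 7.1.2 requires a permanent stop for GI perforation or fistula and for reversible posterior leukoencephalopathy whatever the grade, and for grade 3 infusion reactions. Toxicities it does not name may be held for up to 42 days. A grade 3 infusion reaction with a grade 4 unnamed toxicity is thus a hold under the sentence and a stop under 7.1.2. Section 4.5 repeats these ramucirumab stops. No pair count was made here.

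**The case against.** The strongest reply is that the plan already directs action row by row. Sections 1.4 and 7.2 point to the later detail, 7.2.2 sends the reader to Table 5, and 4.5 cites Table 5 again. An overview sentence is naturally read as escalating to the worst event, not as cancelling a specific permanent stop. The resumption note covers endocrinopathies only, and no visible text authorises restarting after grade 3 pneumonitis, hepatitis, nephritis or myocarditis. This makes the protective reading the likely one in practice. It does not remove the conflict, because the sentence is the plan's only visible rule specific to concurrent toxicities, and it names grade as the deciding factor.

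A second reply is that the General instructions row at the head of Table 5 has no visible content. That is where a precedence rule might stand. A reader might infer that the plan has no such rule; the documents as available do not support that. What can be said is that the sentence and the visible rows disagree.

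A third reply is that four of the eight reversals are stops that 4.5 names on its own. This stands, and it limits the core case to the four hyperglycemia pairings.

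A reader might also take the larger counts (26 of 161, 33 of 189) as the size of the problem. They depend on treating continuation as a modification, which the text does not say. No pair count measures patient risk, because the documents give no co-occurrence rates.

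**Conclusion.** The sentence is wrong as written; severity is minor. It contradicts Table 5 in four core pairings: grade 4 hyperglycemia with beta-cell failure alongside a first grade 3 pneumonitis, hepatic, renal or myocarditis event. Four further pairings reverse on Table 5 but are covered separately by 4.5. The ramucirumab rules in 7.1.2 have the same defect, also with cover in 4.5.

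A reader might infer that patients who meet a stop criterion would be routinely restarted. The documents do not support that. If grades are reassessed, restart requires the organ event to drop below grade 3 while hyperglycemia is still grade 4, and then to reach grade 1 or lower (myocarditis: resolved) by the time hyperglycemia is grade 2 or lower and controlled. Clinicians would probably apply the stricter row anyway. Nor does the point touch the two-stage design, the response-rate analysis or the sample size.

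The conclusion assumes a literal reading, reassessment of grades over time (the plan does not say when the comparison is repeated), and no resolving rule in the part of Table 5 that cannot be seen. Confidence is medium for that last reason.

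**What to change.** First check the full General instructions row of Table 5 for a rule on concurrent events. If it does not settle the matter, replace the sentence in 1.4, 7.1 and 7.2 with:

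*If more than one toxicity occurs concurrently, apply the action specified for each toxicity to each drug separately; where actions for the same drug differ, the most restrictive prevails.*

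All eight pembrolizumab reversals, and the ramucirumab examples, then resolve to the permanent stop. It also settles equal-grade pairs, on which the present sentence is silent. The cost is one sentence in three places at the next amendment, with no extra data, visits or patients and no change to the sample size or analysis.
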